Introduction

Healthcare for older adults with multiple chronic conditions (MCCs) is burdensome and of uncertain benefit, resulting in unwanted and unhelpful care. Patient Priorities Care (PPC) is an approach that aligns care with patients' health priorities (i.e. the health outcomes most desired given the healthcare each is willing and able to receive). PPC offers the opportunity to increase value by improving both outputs (desired health outcomes) and inputs (healthcare preferences) for these major users of healthcare.

The ultimate goal of our work is to implement and evaluate this approach to care for older adults with multiple chronic conditions that focuses on what matters most to them and is less fragmented and burdensome, resulting in better quality and outcomes at lower cost. This study will focus on evaluating practice change at test sites at the Cleveland Clinic.

Background and Significance

The 60-70% of older adults with multiple chronic conditions (MCCs) are major recipients of healthcare.¹ Much of this healthcare is burdensome and of uncertain or modest benefit.² Most evidence is generated in persons with few conditions and assessed by survival or disease-specific outcomes that may not be what matters most to this population who vary in their outcome priorities.²⁻⁸ The burden imposed by caring for MCCs is increasing.^{9,10} Medicare patients with MCCs spend an average 33 days per year in contact with the healthcare system and two hours a day on healthcare-related activities.^{11,12} Cost to the health system (primarily Medicare) accounts for the bulk of the medical spending among older adults. Out of pocket expenses are growing.¹³ Some of this care may be harmful.¹⁴ The uncertain benefit, treatment burden, potential harm, and rising costs all call into question the value of healthcare for older adults with MCCs. True value-based care must be of value to individuals, health systems, and payers.¹⁵ Health systems view value based not only on benefits to the system, but also to the patients they serve. In considering value from a patient's perspective, the personal health outcomes that they hope to achieve – which vary for older adults with MCCs - are the appropriate outputs.^{6,16} The inputs include financial costs and indirect costs in terms of the health-related workload.¹⁶ When defined as what patients are willing and able to do, the indirect costs inform healthcare preferences.¹⁷ Patients' desired health outcomes given their healthcare preferences constitute their health priorities.¹⁷⁻²⁰ Patient Priorities Care aligns healthcare with patients' health priorities.¹⁷⁻²⁰ We now aim to evaluate its value within the Cleveland Clinic.

Healthcare utilization and costs associated with age and MCCs are well known.^{1,21} Persons ≥ 65 years are 15% of the U.S. population but consume 34% of health care expenditures, including both community-based care and hospitalization.^{21,22} Approaches for improving care of older adults with MCCs have been investigated.²¹⁻²⁵ A systematic review of 18 systems- or patient-based interventions - none addressing patients' priorities - revealed modest effect on patient-reported outcomes but little or no effect on

healthcare utilization; cost data were limited.^{24,25} Some interventions targeting specific health problems, particularly among persons with advanced illness, have proven cost-effective in the hospital setting; less is known about cost-effectiveness in the ambulatory setting.²⁶⁻³⁵

Compared to patients receiving usual care (UC) in a recent study, those receiving PPC reported greater decrease in treatment burden (a major concern for older adults with MCCs), had more medications stopped and fewer self-management tasks and diagnostic tests ordered.³⁶

To determine the value of PPC, comparable primary care sites within the Cleveland Clinic will be assigned to PPC or UC. Clinicians and staff at the PPC site will be trained to identify and align decision-making with the health priorities of older adults with MCCs. Value will be compared using patient and provider-reported outcomes, healthcare utilization, and possibly costs at PPC and UC sites.

Hypothesis/Research Question

Does aligning healthcare with patients' health priorities (their most desired health outcomes given the healthcare activities they are willing and able to do) increase value?

Study Design

Methods

We will employ a quasi-experimental, usual care (UC) group design, involving 2 primary care sites (1 PPC and 1 UC). Patients are assigned to intervention or usual care arms based on their primary care practice location. We will use analytic techniques (e.g., inverse propensity score weighting) designed to reduce selection bias and balance PPC and UC sites in terms of baseline characteristics. Data collection will occur through quantitative and qualitative interviews and health encounter information in the EHR.

Patient Priorities Care requires the elicitation and documentation of patient health outcome goals and care preferences and the alignment of clinical care with goals and priorities to achieve patients' health outcome goals and reduce the burden of multi-morbidity. Participants will be enrolled in the Patient Priorities Care Program and speak with a trained health priorities facilitator to elicit their healthcare preferences and health outcome goals, which together constitute their health priorities. This information will be documented, entered into the EHR, and shared with the clinicians who will then use the Patient Priorities Care approach with patients to inform and guide treatment decisions. Patients will participate in the program and be followed for up to one year from the health priorities identification visit.

Sample

Patients: Potentially eligible participants for this project include Medicare beneficiaries (Traditional, Medicare Advantage, and dual eligible) 66 years or older who are patients of participating clinicians.

We assessed the power to detect clinically relevant differences in Patient-Reported Outcomes (PROs) and categories of healthcare utilization, both needed to measure value. We calculated minimal detectable differences for the primary PPC outcomes based on a sample size of 500 participants (250 PPC and 250 in UC) that assumed 80% power, a one-tailed alpha of 0.05, and an R-squared of 0.2 from other covariates. Assuming a standard deviation of 24.1 at pre-test and 17.6 at post-test and a correlation between measurement pairs of 0.55 (based on pilot data) allows us to detect a between-group difference in mean change in the TBQ score from pre-test to post-test of -4.6 points.³⁷ Comparing the PPC group to the UC care group, our sample permits us to detect an odds ratio of 1.7 with respect to discontinuing medications and an odds ratio of 0.52 with respect to having diagnostic tests ordered.³⁸

Inclusion/Exclusion Criteria

The evaluation of PPC in the clinical practice will take place as part of the patient's ongoing healthcare, and is minimal risk. Criteria for inclusion in the clinical program will be expansive in order to offer the opportunity for the largest number of reachable patients possible. All recruits will be those who are currently patients at Cleveland Clinic. Patient's meeting any of the exclusion criteria will not be approached by the Cleveland Clinic clinicians.

Inclusion Criteria:

1. Age 66 and older
2. In the Cleveland Clinic patient population
3. In the clinician practices selected as intervention or usual care practice sites
4. Clinically identified by: Those who meet any of several criteria
 - i. 3 chronic conditions (See appendix 0 for the complete list)
 - ii. 10 medications
 - iii. >2 ED visits over the past year
 - iv. >1 hospitalization (or >10 days in hospital)
 - v. receive any care coordination services
 - vi. 2 specialists over past year

Exclusion Criteria:

1. In hospice or meeting hospice criteria for any condition
2. Advanced dementia or moderate to profound intellectual disabilities
3. Not English speaking
4. Nursing home resident

Primary Care providers (PCPs) and Health Priorities Facilitators: PCPs are identified at the intervention site by screening the clinic's electronic health records (EHR) to identify those clinicians with eligible patients in their clinic panels. This requires a waiver of consent and waiver of HIPAA authorization. Potential priorities facilitators were identified by examining existing resources and finding most appropriate care givers within the facility (Appendix.1). Employee Study Information sheet will be personally distributed in advance. Research team will directly contact potential clinicians and facilitators, and allow them to review our intervention and expected roles. If potential clinicians and facilitators express interest in the project, they will be also asked to confirm their willingness to complete one hour over-the-phone training session and one half-day training session to be familiar with the intervention process in addition to review of online training materials. At this point, no protected health information or patient identifying information is collected or recorded.

Procedures

The subject for this IRB protocol is the implementation and evaluation of the Patient Priorities Care process that will be implemented in clinical sites at the Cleveland Clinic (CC). The CC Patient Priorities Care team including, primary physicians, and health priorities facilitators (i.e. Geriatrician, Medical Assistant, Care Coordinators, and Patient Liaison Program Coordinators, Nurse practitioners) along with other logically necessary individuals, will help patients elicit their health outcome goals and healthcare preferences. The elicitation of patient priorities will be embedded into CC clinical programs routinely offered to patients (Appendix 1).

Table 1. Schedule of Evaluation for Patient Population

Clinical Procedures				Goal Facilitation Visit(s)	PPC Clinician Visit(s)	Goal Facilitator Follow up		
Research Procedures		Pre-Screening	Baseline Interview				Follow up interview	Follow up
	Week	Up to -7	-5 to 0	-6 to -1	0	2 to 6 (1-2wk after 1 st PCP)	34 to 52	Up to 52
	Month		-1	-1	0	1-2	8 – 12	12
Intervention arm	Consent		x				x	
	EHR data extraction		x					x
	Identification/ discussion of patient health priorities			x	x	x		

	Interview 
 • Demographics • 5-word recall* • PROMIS • CollaboRATE • Tx Burden questionnaire 		x					x	
	PCP visit			x					
Usual care arm	Interview 
 • Demographics • 5-word recall* • PROMIS • CollaboRATE • Tx Burden questionnaire 		x				x		
	PCP visit				x		x	x	
	EHR data extraction		x						x

*Baseline in-person interview only.

Patients meeting criteria within the Cleveland Clinic Lakewood Family Health Center (FHC) and Brunswick FHC patients who are scheduled to have visit during study period will be recruited using mail, or My Chart message about the project taking place. Lakewood FHC will be serving as intervention site and Brunswick FHC as usual care. Eligible and consented patients will participate in the program and be followed for up to one year from the goal elicitation visit. Primary physicians, and priorities facilitators (i.e. Geriatrician, MAs, Care Coordinators, Patient Liaison Program Coordinators, and Nurse practitioners) will undergo training and preparation to elicit and provide care aligned with health priorities. This training has been developed and tested during the Yale University pilot study of Patient Priorities care.

Pre-screening and Recruitment (Research procedure)

A list of patients meeting above criteria will be generated by the methods described below, and provided to PCPs to obtain their permission to invite patients. PCPs may suggest removing any patients who may not be appropriate for the intervention at PCP's discretion. Research team will conduct a baseline interview after obtaining verbal consent from the patients. Priorities Facilitators will be notified to invite these patients to have their health priorities identified and their care aligned with these priorities. To maximize flexibility and align with current workflow, the invitation for priorities identification can be during a regular visit, by phone, by mail, or other means already used by the practices (e.g. same visit as invitation; part of annual wellness visit, etc.).

Project specific generated list: Each week, a scheduling system will provide an automated list of targeted patients with appointments 6 weeks later. Appointment types include in-person office visit, distance health, virtual, or telephone visit. This system is linked with EHR and widely used at our institution. Once target patients are identified and approved by the PCP, research personnel will contact via mail, or My Chart messaging to introduce the Patient Priorities Care program with an information sheet to explain the Patient Priorities Care process and ask them to contact the research team if they want to opt out. Opt-out patients will be recorded in the screening log to avoid contacting again for future recruitment.

Care providers referral: Care providers can make a referral if they have patients who could benefit from the Patient Priorities Care program, otherwise meet inclusion and exclusion criteria, and have regular visits in next few months. Care providers can discuss the program and provide information sheet to the potential participants. Clinician will notify the research team of the potential patients who have agreed to participate in the PPC. Research team will contact these potential participants to obtain consent to participate in Patient Priorities Care before asking any research questions. Care providers will also notify names of patients who decline to participate in order to avoid contacting the same patients again for future recruitment.

Primary Care Coordination patients list: For patients enrolled through the Care Coordination program, research personnel will identify the individuals ahead of time and obtain permission from their PCPs. Research team will contact via mail, or My Chart messaging to introduce the Patient Priorities Care program with an information sheet to explain the Patient Priorities Care process and ask them to contact research team if they want to opt out. After excluding patients who opted out, research personnel will contact patients to obtain consent and conduct baseline interview. Because this project provides prioritized patients' list based on their existing Care Coordination patient list for the Coordinators to reach out, this process adds very little burden on Care Coordinator's part.

Usual care Group

Concurrent to the Patient Priorities Care implementation, we will begin to identify the usual care group which will include up to 250 patients. We will identify a sample similar to the intervention group, using the same inclusion/exclusion criteria and clinical judgment. The usual care group will be identified from Brunswick FHC patients.

The usual care group will be identified through the same electronic health record search and Care Coordination patient list described above, and PCPs will have the option of not including any of their patients for interview for usual care group.

The usual care group during the study period will receive a recruitment letter from their clinician

describing the research and interview. Patients will be able to opt-out if they do not wish to be contacted by contacting research team listed in the invitation letter. For patients who do not opt-out, a centralized, trained research personnel will contact candidates by phone to confirm eligibility and to obtain verbal consent for enrollment in the usual care arm which involves standard clinical care, data collection through an interview, and a medical record review.

Consent process

We will require a full waiver of consent and HIPAA authorization for the health care utilization data that will be used as part of the screening process and evaluation of the patient population. We will also request a waiver of signed consent and HIPAA authorization for participation of clinicians and patients in the research evaluation. It would be impractical to gain signed consent for this information, specifically for this population and the research involves minimal risk.

Consent process will be conducted primarily over the phone by a trained project staff member. Patients will be notified via letter, My Chart message or phone that a CCF research personnel will be contacting them to conduct the interviews. A trained research coordinator will administer the qualitative survey. Participants in both intervention and usual care groups will receive \$10 for each research interview for a total reimbursement of up to \$20.

Baseline interview

Once potential patients are identified, research personnel will add participants' contact information into a secure electronic data collection system (REDCap) which the research team will also use to contact the participants to administer the interview. Up to 6 weeks prior to their next PCP appointment, selected patients will be contacted by phone or in-person to confirm consent to participate. Once eligibility is confirmed, research personnel conduct phone or in-person baseline interview whichever is preferred by the patient. Baseline interview could follow after Priorities Facilitators (Geriatrician, MA, Care coordinator, Patient Liaison Program Coordinators, Nurse Practitioners) completes priorities identification process. This can be done before or the day of the initial PCP visit to begin deciding treatment plans based on priorities. Contact information will be stored separately from interview and medical record data and destroyed once the follow-up interviews have been conducted and data collection and cleaning is complete.

Priorities Facilitators will help patients identify their health priorities, complete the health priorities template in EHR. Please note that similar process has been routinely done at the clinic as part of Care Coordinators' and Patient Liaison Program Coordinators' job (Appendix 1), and this project provides more structure in documentation and collaboration with other care providers involved.

PCPs will be asked to review the patients' health priorities at subsequent clinical follow up visits and update if necessary.

At the intervention site, we will identify site champions to develop continued buy-in from providers (e.g., staff meetings, individual meetings, case examples), obtain feedback, and notify the PI and research team of unanticipated problems.

Intervention (Clinical procedure)

Patient Priorities Care is an innovative approach to shared decision-making that draws from existing professional training (e.g. clinical competencies, motivational interviewing, and geriatrics care). Patient Priorities Care requires the elicitation and documentation of patient health outcome goals and care preferences and the alignment of clinical care with health goals and healthcare preferences (collectively referred to as health priorities) Participants will be enrolled in the Patient Priorities Care Program and communicate with a trained priorities facilitator in-person or over the phone to elicit their health priorities. This information will be documented in the PPC- GOALS AND PREFERENCES form in the EHR and shared with the clinicians who will then use the Patient Priorities Care approach with patients to inform and guide treatment decisions.

Patients will participate in the program and be followed for up to one year from the priorities elicitation visit by the research team. The target follow-up time is 8-10 months. The PCPs will be trained in decisional strategies that have been shown to help align care with patients' health priorities. While encouraged to use these decisional strategies, PCPs will be free to make the recommendations they feel most appropriate for each patient.

This intervention has been developed to be integrated seamlessly into usual care, and does not involve any research aspect such as program development, data collection, and evaluation at all. Documentation completed by Facilitators is considered part of standard clinical care. Intervention development, data collection and evaluation including follow up data collection are conducted by the research team. What PCPs and facilitators are asked to perform for this project is within their standard scope of work. The intervention does not require additional visits or substantially increased provider time for PCPs as the Goals and Preferences information collected by the Facilitator will be used as decision aid during regular office visits. However, it is to the providers' discretion, to spend as much time as needed if that would benefit the participating patient.

Priorities Facilitators

The Priorities Facilitators will be trained health professional (i.e. Geriatrician, MA, Care Coordinators, and Patient Liaison Program Coordinators, Nurse practitioners).

Responsibilities

1. Undergo training and preparation to elicit and document patients' health priorities
2. Elicit priorities using PPC point-of-care materials.

3. Provide a copy of completed PPC- GOALS AND PREFERENCES form to the PCP before the PCP visit and encourage patients to bring this up during their PCP visit.
4. Communicate these health priorities to the Primary Care Provider through verbal discussion and/or documentation into the patient's Electronic Health Record (EHR). prior to the PCP visit.
5. Enter the identified health priorities into Electronic Health Record (EHR) and provide to patients (as applicable).
6. Contact enrolled patients to follow up 2-3 weeks after the initial PCP visit and assist in building a partnership between patient and clinician.
7. Review health priorities and update as needed

Clinicians

The clinician will be a licensed health care professional (MD, APRN, PA). Visits can be in-person, virtual, or phone visits.

Responsibilities

1. Participate in health priorities aligned care training that includes a 2 hour face to face session followed by ongoing short review sessions
2. Know or review patient's health priorities template provided by the priorities facilitators, align care decisions to each patient's health priorities ”
3. Decision making moves
 - a. From: *You need (fill in blank) for your (fill in blank).*
 - b. To: *There are different things that we could do. But knowing your conditions, your overall health, and your health outcome goals and care preferences (what matters most to you), I suggest we try (fill in the blank).*
4. Translate patient's health priorities into care options with guidance from point-of-care materials, decisional guidance and strategies, , and clinician champions
5. Participate with patients/caregivers in shared decision-making around health priorities
6. Review, discuss, and update patient's health priorities or refer to priorities facilitator for further discussion
7. Include patient health priorities in clinical communications such as referrals, consults, and clinical notes.
8. Discuss with specialists (e.g. cardiologists) as needed to ensure care is aligned with patient's priorities
9. Document discussions and decisions in EHR (SMART phrases)

Follow up data collection (Research procedure)

Follow up data collection will be two-fold: We'll conduct phone (or in-person) interview and ask the same questions except cognitive ability screening items at 8-10 months from the baseline; and we'll collect patient-level utilization and other clinical variables from EHR from 3 months prior to baseline date through up to 12 months after the baseline date.

Follow up interview: Approximately 9 months from the PCP visit, follow up interview will be conducted by phone or in-person. All patients who participated in the intervention will be contacted at 9 month (+/- 30 days protocol window) to complete follow up interview defined in the variable list. A week prior to follow up interview period, research personnel will send mail/My Chart message or call to remind participants of the follow up interview session. If participant does not respond to the follow up interview invitation by the 9th month, we will follow up with a letter with the interview form and self-addressed, stamped envelope enclosed. We will ask patients to fill the forms and send back by mail.

Post-Follow up interview: Research personnel will contact enrolled patients who completed follow up interview for missed question items from the follow up interview by calling messaging. If an enrolled participant does not respond to the Post-follow up interview invitation by the 12th month from baseline, we will follow up with MyChart message or a letter with the interview form and self-addressed, stamped envelope enclosed. We will ask patients to fill the forms and send back by MyChart message link or mail. This procedure only apply to enrolled patients who completed follow up interview but missed questions due to Redcap programing error reported on 7/15/2021 as Unanticipated Problem.

Data extraction: From 3 months prior to Baseline Interview through up to 1 year from the Baseline Interview, the following information will be ascertained from patients who gave consent: The number and types of chronic conditions (collected at Baseline only), medications, Healthcare activities defined as below, ACP (Advance Care Planning) tab use, and the Accountable Care Organization (ACO) survey as defined below.

Data Collection overview

In the 2 participating sites (Lakewood and Brunswick) the following information will be collected:

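### Usual-care patients are identified with an undefined clinical-judgment step, and PPC has a referral route that usual care lacks, so selection in the two arms is discretionary and unmatched.

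*Protocol*

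**What the plan says.** Allocation is not randomised: "Patients are assigned to intervention or usual care arms based on their primary care practice location" (Protocol, Methods). Lakewood is the intervention site. For the controls, "The usual care group will be identified from Brunswick FHC patients" (Protocol, Usual care Group).

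The Usual care Group section gives the selection rule: "We will identify a sample similar to the intervention group, using the same inclusion/exclusion criteria and clinical judgment". Its next paragraph gives the sources, "The usual care group will be identified through the same electronic health record search and Care Coordination patient list described above", and then a physician option: "PCPs will have the option of not including any of their patients for interview for usual care group". An opt-out letter and a call from central research staff follow.

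For PPC, Pre-screening and Recruitment describes three routes:

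- a weekly list, in which "a scheduling system will provide an automated list of targeted patients with appointments 6 weeks later";
- the Care Coordination list;
- provider referral: "Care providers can make a referral if they have patients who could benefit from the Patient Priorities Care program".

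The same section allows physicians to take patients off the list: "PCPs may suggest removing any patients who may not be appropriate for the intervention at PCP's discretion". The SAP (Setting and Population) repeats the removal step but mentions neither clinical judgment nor referral. For imbalance, the SAP relies on inverse probability of treatment weights, with a balance threshold of .25 in absolute standardized mean difference, and on adjustment for the baseline outcome value and for demographic and clinical characteristics.

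**The concern.** In the control-selection sentence, judgment stands beside the entry criteria as something additional, and its stated aim is resemblance to the other arm. No person, criterion, time or record is attached to it. The shared sources settle who could be sampled. They do not settle who is approached, because the protocol never says that all listed patients are contacted, or that they are contacted in sequence or at random, and the arm is capped at up to 250. Undefined judgment can act in that gap, exercised by people who know the arm.

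The PPC side does not mirror this. It has a referral route based on expected benefit from the program, and its removal wording is tied to suitability for the intervention. The usual-care removal option has no stated criterion.

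With one site per arm and no randomisation, comparability depends heavily on how patients enter. Judgments of this kind can draw on traits that are not recorded, such as frailty, engagement or outlook. Weighting and regression balance only what is measured. A residual difference could therefore affect any of the four primary outcomes, in either direction.

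**Working it through.** **1. Selection steps side by side**

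| Step | PPC (Lakewood) | Usual care (Brunswick) |
|---|---|---|
| EHR/appointment list | Yes | Yes (same search) |
| Care Coordination list | Yes | Yes |
| Provider referral on expected benefit | Yes | Not named |
| Clinical judgment toward similarity | Not stated | Stated, undefined |
| Physician removal | Yes, tied to suitability for the intervention | Yes, no criterion |
| Rule for which listed patients are approached | None stated | None stated |

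Both arms have discretion, but of different kinds.

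**2. The plan's own figure, for scale**

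Inputs (Protocol, Sample): TBQ SD 24.1 before and 17.6 after, correlation 0.55, 250 per arm, 80% power, one-tailed alpha 0.05.

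- SD of change = √(24.1² + 17.6² − 2 × 0.55 × 24.1 × 17.6) = 20.59.
- Detectable difference = (1.645 + 0.842) × 20.59 × √(2/250) = 4.58.

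This matches the stated 4.6 points when the R-squared of 0.2 is not applied. The figure does not depend on the present point.

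**3. Illustration of bias**

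The documents give neither input, so both are assumptions:

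- d = 0.25 SD, the shift in an unrecorded trait. It equals the imbalance the SAP tolerates for measured covariates and is otherwise arbitrary.
- r = 0.2 to 0.3, the partial correlation of that trait with the outcome.

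Bias in SD units = d × r:

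- 0.25 × 0.2 = 0.05
- 0.25 × 0.3 = 0.075

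The value in TBQ points depends on the SD used:

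| SD | Value | Bias in points |
|---|---|---|
| Post-test, adjusted for baseline: 17.6 × √(1 − 0.55²) | 14.7 | 0.7 to 1.1 |
| Post-test | 17.6 | 0.9 to 1.3 |
| Change | 20.59 | 1.0 to 1.5 |

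**4. Effect on a one-sided 5% test with no true effect**

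The standard error in SD units is √(2/n). With 125 per arm (SAP, Setting and Population) it is √(2/125) = 0.126. Error = P(Z > 1.645 − bias/SE) if the bias favours PPC, and P(Z > 1.645 + bias/SE) if it goes against PPC.

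| Bias | Bias/SE | Favours PPC | Against PPC |
|---|---|---|---|
| 0.05 SD | 0.395 | P(Z > 1.250) = 10.6% | P(Z > 2.040) = 2.1% |
| 0.075 SD | 0.593 | P(Z > 1.052) = 14.6% | P(Z > 2.238) = 1.3% |

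At the protocol's 250 per arm, SE = 0.0894. The same biases give about 14% and 21% in one direction and 1.4% and 0.7% in the other. The calculation treats patients as independent and unweighted.

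**5. Sensitivity to the assumptions**

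Using the change SD, d from 0.1 to 0.5 and r from 0.1 to 0.5 give:

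- lowest: 0.1 × 0.1 × 20.59 = 0.2 points
- highest: 0.5 × 0.5 × 20.59 = 5.1 points

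The low end is negligible and the high end exceeds the 4.6-point detectable difference. The size is therefore unknown.

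**The case against.** The best defence is that clinical judgment may simply mean the physician option in the next paragraph, the only discretion described as an operating step for usual care. That reading is possible. However, the sentence has the study team as its subject, and the physician option is stated separately with a different actor. If nothing more was meant, a clarifying sentence is still needed.

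The defence is right that several stronger readings go too far:

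- *Controls are picked by hand.* A reader might infer this from the wording about similarity. The text describes an EHR search, an existing list, an opt-out letter and a central call. No step has staff choosing individuals for resemblance to PPC patients.
- *Only the control arm is subject to judgment.* The weekly list is one of three PPC routes. Referral is explicit case-by-case judgment, and physicians may also remove PPC patients.
- *Controls are chosen before a PPC group exists.* The protocol describes concurrent identification, so the PPC group is still accruing. It is a moving target for similarity, but not an absent one.
- *The sentence is what reveals the arm.* Knowledge of the arm follows from allocation by site.
- *False-positive error is inflated.* That depends on a sign the documents do not give; the opposite sign lowers it.

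It is also fair to say that the SAP speaks of the limited sample in the past tense, so recruitment may be over. In that case changing the wording will not change who was enrolled.

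**Conclusion.** The point stands as a weakness in how patients are selected. An undefined judgment step lies between the shared list and the approached usual-care sample. PPC has a discretionary referral route not named for usual care. The two removal provisions are worded differently. Any resulting difference in unrecorded traits is outside the reach of the planned weighting and adjustment.

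Neither the direction nor the size can be derived from the documents. Under the assumed 0.25 SD shift and r of 0.2 to 0.3, the bias is 0.05 to 0.075 SD, or roughly 0.7 to 1.5 TBQ points depending on the SD used. One-sided error at 125 per arm becomes about 11–15% or about 1–2%. These figures show that modest selection could matter; they are not evidence that it occurred. The change is worth making because one common rule is cheap and leaves less to argue about in a two-site comparison.

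**What to change.** **If enrolment is open**

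1. Delete the reference to clinical judgment from the Usual care Group section.
2. At both sites, approach all patients who meet the criteria from the same two sources (weekly appointment list and Care Coordination list), in order of appointment date, until the site target is met. Leave similarity to the pre-specified weights.
3. State one physician-removal rule with the same wording at both sites.
4. Log every listed patient not approached, with the reason, by site.
5. Flag PPC patients who entered by provider referral, and add to the SAP a sensitivity analysis without them.

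**If enrolment is complete**

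Report by site how many patients were listed, passed over by judgment, removed by the physician, referred and enrolled, or state that this was not recorded. Add the same sensitivity analysis.

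**Cost**

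The change needs edits to Pre-screening and Recruitment and to Usual care Group, plus a short SAP addition. It brings slightly more logging and analysis, and less flexibility in filling the usual-care arm. Both lists are already planned sources. Retrospective counts depend on records that the documents do not describe, apart from the screening log of opt-outs.
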